### **9.8.2 Rash**

Individuals who develop a generalized rash will be monitored closely. Study drug dosing should be interrupted if a subject develops a generalized rash of Grade 3 or higher, or a rash that is considered a serious adverse event (SAE). The investigator will notify the medical monitor of any rash that results in interruption of study drug, is Grade 3 or higher (Section 13.1.1.4), or is an SAE. Investigators should consider additional evaluation including laboratory testing (e.g., complete blood count [CBC] with differential, LFTs), photographs of the rash, and dermatology consultation. The investigator may consider resumption of study drug if considered clinically appropriate.

## **9.9 Removal of Subjects**

Subjects may withdraw from the study at any time at their own request. Subjects may be withdrawn from study drug treatment at any time at the discretion of the investigator or Vertex for safety, behavior, noncompliance with study procedures, or administrative reasons. A subject who withdraws from study drug treatment will continue to be followed unless the subject withdraws consent (and assent, as applicable).

In addition, a subject must be discontinued from study drug treatment if the subject meets any of the following criteria:

- Has a screening *CFTR* genotype that does not confirm study eligibility if a previous *CFTR* genotype laboratory report was used to establish eligibility. These subjects must be discontinued from the study (Section 8.1)
- Meets any of the stopping (discontinuation) criteria (Section 9.8)
- Becomes pregnant (Section 11.6.7.2)

Subjects who discontinue study treatment early should continue to return for study assessments, as noted in Section 9.1.5.

If a subject does not return for a scheduled visit, reasonable effort will be made to contact the subject. In any circumstance, reasonable effort will be made to document subject outcome. The investigator will inquire about the reason for withdrawal, request that the subject return all unused investigational product(s), request that the subject return for an ETT Visit and Safety Follow-up Visit, if applicable (see Section 9.1.4), and follow up with the subject regarding any unresolved AEs.

If a subject withdraws consent or assent for the study, no further assessments will be performed. Vertex may retain and continue using the study data and samples after the study ends, and may use the samples and information in the development of the study compound, for other drugs and diagnostics, in publications and presentations, and for education purposes. If a subject withdraws from the study, the study data and samples collected will remain part of the study. A subject will not be able to request the withdrawal of his/her information from the study data. A subject may request destruction of the samples collected from him/her during the study as long as those samples can be identified as his/her samples.

### **9.10 Replacement of Subjects**

Subjects who withdraw or are withdrawn before the first dose of study drug on Day 1 of the Treatment Period may be replaced.

Subjects who withdraw or are withdrawn for nonsafety reasons during the study drug treatment period may be replaced at Vertex's discretion.

## **10 STUDY DRUG INFORMATION AND MANAGEMENT**

During the Run-in Period, study drug refers to ELX/TEZ/IVA and IVA.

During the Treatment Period, study drug refers to VX-121/TEZ/D-IVA and matching placebo, ELX/TEZ/IVA and matching placebo, and IVA and matching placebo.

### **10.1 Preparation and Dispensing**

Study drug may be dispensed only under the supervision of the investigator or an authorized designee and only for administration to the study subjects.

## 10.2 Packaging and Labeling

Study drug tablets will be supplied in blister cards by Vertex. Study drug labeling will be in compliance with applicable local and national regulations. Additional details about packaging, labeling, and dispensing for study drug will be in the Pharmacy Manual.

## 10.3 Study Drug Supply, Storage, and Handling

VX-121/TEZ/D-IVA will be supplied as FDC film-coated tablets containing 10 mg VX-121/50 mg TEZ/125 mg D-IVA. Matching VX-121/TEZ/D-IVA placebo tablets will be of similar size and appearance and contain 0 mg VX-121/0 mg TEZ/0 mg D-IVA (Table 10-1).

ELX/TEZ/IVA will be supplied as FDC film-coated tablets containing 100 mg ELX/50 mg TEZ/75 mg IVA. Matching ELX/TEZ/IVA placebo tablets will be of similar size and appearance and contain 0 mg ELX/0 mg TEZ/0 mg IVA (Table 10-1).

IVA will be supplied as a tablet containing 150 mg IVA. Matching IVA placebo tablets will be of similar size and appearance and contain 0 mg IVA (Table 10-1).

Blister cards must be stored under conditions noted in the Pharmacy Manual. The investigator, or an authorized designee (e.g., a licensed pharmacist), will ensure that all investigational product is stored in a secured area, under recommended storage conditions, and in accordance with applicable regulatory requirements. To ensure adequate records, all study drugs will be accounted for via the drug accountability forms as instructed by Vertex.

**Table 10-1 Study Drug; Strength/Dosage Form/Route**

Drug Name, Dosage Form, Route	Strength
VX-121/TEZ/D-IVA, FDC tablet, oral	
VX-121	10 mg
TEZ	50 mg
D-IVA	125 mg
VX-121/TEZ/D-IVA-matching placebo, tablet, oral	0 mg
ELX/TEZ/IVA, FDC tablet, oral	
ELX	100 mg
TEZ	50 mg
IVA	75 mg
ELX/TEZ/IVA-matching placebo, tablet, oral	0 mg
IVA, tablet, oral	150 mg
IVA-matching placebo, tablet, oral	0 mg

D-IVA: deutivacaftor; ELX: elexacaftor; FDC: fixed-dose combination; IVA: ivacaftor; TEZ: tezacaftor

## 10.4 Drug Accountability

The pharmacist or designated study site staff will maintain information about the dates and amounts of (1) study drug received; (2) study drug dispensed to the subjects; and (3) study drug returned by the subjects. Subjects will be instructed to return all used and unused materials associated with the study drug to the site. These materials will be retained at the site according to instructions provided by Vertex or its designee. The study monitor will review study drug records and inventory throughout the study.

If a site uses a site-specific drug accountability system and/or process, including processes associated with the destruction of returned materials, the process must be documented and approved by Vertex. Additional details will be provided in the Pharmacy Manual. The study monitor must review the drug accountability documentation on a regular basis. The study monitor will promptly communicate to Vertex any discrepancies he/she is unable to resolve with the site.

### **10.5 Disposal, Return, or Retention of Unused Drug**

The study site staff or pharmacy personnel will retain all materials returned by the subjects until the study monitor has performed drug accountability. The investigator will ensure that the materials are destroyed in compliance with applicable environmental regulations, institutional policy, and any special instructions provided by Vertex. Destruction will be adequately documented.

The principal investigator (PI), study site staff, including pharmacy personnel will assist Vertex with any recall activities (as applicable) and place impacted investigational medicinal product (IMP) in quarantine when requested.

### **10.6 Compliance**

To ensure treatment compliance, the investigator or designee will supervise all study drug dosing that occurs at the site. At each visit, site personnel will review that the subject is compliant with study drug dosing and remind the subject of study drug dosing requirements. Compliance will also be assessed by ongoing study drug count.

If a subject demonstrates continued noncompliance of study drug dosing despite educational efforts, the investigator should consider discontinuing the subject from the study.

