**Table 3-2 Study VX20-121-103: Run-in Period, Treatment Period, and Safety Follow-up Visit**

Event/Assessment a	Run-in Period		Treatment Period b						ETT Visit c	Safety Follow-up Visit 28 (± 7) Days After the Last Dose of Study Drug (If Applicable) d	Comments
	Day -28 (± 1 Day)	Day -14 (Day -15 to Day -3)	Day 1	Day 15 (± 3 Days)	Weeks 4, 8, 12, 16 (± 5 Days)	Weeks 20, 28, 32, 40, 44, 48 (± 5 Days)	Weeks 24 and 36 (± 5 Days)	Week 52 (± 5 Days)			
Clinic visit	X	X	X	X	X e		X	X	X	X	See Section 9.1.8 for use of remote measures in extenuating circumstances.
Telephone contact						X					Assess the subject’s status, any AEs, concomitant medications, treatments, and procedures.
Inclusion and exclusion criteria review	X										Section 8
Randomization			X								Randomization may occur on either Day -1 or Day 1, after all eligibility criteria are confirmed (Section 9.1.3).
CFQ-R			X		Weeks 8 and 16		Week 24	X	X		Completed before the start of any other assessments on the day of the study visit (Section 11.5.3).

a All assessments will be performed before dosing unless noted otherwise.

b To enter the Treatment Period, conditions for entry must be satisfied (Section 9.1.3).

c If the subject prematurely discontinues study drug treatment, an ETT Visit should be scheduled as soon as possible after the decision to discontinue treatment (Section 9.1.5). Subjects who prematurely discontinue treatment during the Run-in Period will complete an ETT Visit and Safety Follow-up Visit, as applicable. Subjects who prematurely discontinue study drug treatment during the Treatment Period should continue to complete all scheduled study visits for assessments following completion of the ETT Visit (and Safety Follow-up Visit, if applicable).

d The Safety Follow-up Visit is required for all subjects, unless otherwise specified (Section 9.1.4). For subjects who complete an ETT Visit 3 weeks or later following the last dose of study drug, the ETT Visit will replace the Safety Follow-up Visit, and a separate Safety Follow-up Visit will not be required (Section 9.1.5).

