### **9.1.3 Treatment Period**

Treatment Period assessments are listed in Table 3-2.

The Treatment Period will be randomized, double-blind, and ELX/TEZ/IVA-controlled. It will last approximately 52 weeks (Day 1 through Week 52). Study drug administration details are provided in Section 9.6.

Randomization will occur before the first dose of study drug during the Treatment Period and may occur on either Day 1 or Day -1. Randomization and stratification details are provided in Section 9.2.

To enter the Treatment Period, subjects must have stable CF disease (as judged by the investigator) and have remained on a stable CF treatment regimen during the Run-in Period. Female subjects also must have a negative pregnancy test at Day 1 before receiving randomized study drug. If these conditions are not met (for example, if the subject has an acute upper or lower respiratory infection, PEx, or changes in therapy [including antibiotics] for sinopulmonary disease within 28 days before the Day 1 Visit [first dose of study drug in the Treatment Period]), the subject is considered a run-in failure and cannot enter the Treatment Period or rescreen.

The Week 12 Visit may be performed either in the clinic or as a home health visit, if permitted by local regulations. All home health visits must have a consultation between the subject and investigator (i.e., in person, phone, or telemedicine video conference). This consultation should occur within 2 business days before or after the home health visit and can be outside the visit window. Additional details regarding home health visits will be provided in the Study Reference Manual.

Subjects who prematurely discontinue study drug treatment will remain in the study from the time of discontinuation of study drug treatment through the last scheduled study visit (Section 9.1.5).

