#### **9.1.5 Early Termination of Treatment**

If a subject prematurely discontinues study drug treatment, an Early Termination of Treatment (ETT) Visit should be scheduled as soon as possible after the decision to discontinue treatment. Subjects who prematurely discontinue treatment will also be required to complete the Safety Follow-up Visit, approximately 28 ( $\pm$  7) days after their last dose of study drug.

If the ETT Visit occurs 3 weeks or later following the last dose of study drug, then the ETT Visit will replace the Safety Follow-up Visit, and a separate Safety Follow-up Visit will not be required.

If a subject withdraws consent for the study, no further assessments will be performed. Vertex may retain and continue using the study data and samples after the study ends, and may use the samples and information in the development of the study compound, for other drugs and diagnostics, in publications and presentations, and for education purposes. If a subject withdraws from the study, the study data and samples collected will remain part of the study (Section 9.9).

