##### **9.1.5.2 Discontinuation During the Treatment Period**

Subjects who prematurely discontinue study drug treatment during the Treatment Period should continue to complete all scheduled study visits for assessments following completion of the ETT Visit (and Safety Follow-up Visit, if applicable), as detailed in Table 3-2.

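### Protocol 10.6 points to study removal for persistent dosing noncompliance, while the rest of the protocol stops drug only and keeps randomized subjects' visits; the effect is likely very small

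*Protocol*

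**What the plan says.** Protocol 10.6 covers continued noncompliance with dosing after educational efforts. In that case "the investigator should consider discontinuing the subject from the study". The section does not mention further visits and does not refer to 9.9.

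Protocol 9.9, the section on removal, says that a subject can be "withdrawn from study drug treatment at any time at the discretion of the investigator or Vertex for safety, behavior, noncompliance with study procedures", among other reasons. It continues: "A subject who withdraws from study drug treatment will continue to be followed unless the subject withdraws consent". The only study-level removal it imposes on a subject who has not withdrawn consent is for a genotype that fails confirmation.

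Three other places agree with 9.9:
- Protocol 9.1.3: subjects who stop drug early "will remain in the study from the time of discontinuation of study drug treatment through the last scheduled study visit".
- Protocol 9.1.5.2: those who stop "during the Treatment Period should continue to complete all scheduled study visits for assessments following completion of the ETT Visit".
- Protocol Table 3-2, footnote c, gives the same instruction.

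SAP 8.3.1.2 applies the treatment policy strategy to treatment discontinuation before Week 24, so ppFEV1 observed afterwards is used if available. SAP 8.3.2.2 carries the same handling to the SwCl key secondary endpoints.

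**The concern.** A randomized, dosed subject stays in the Full Analysis Set whatever happens to adherence. A treatment-policy estimand needs that subject's Week 16 and Week 24 values, on or off drug. Section 9.9 and its companions secure those values; 10.6, read literally, lets a site stop collecting them while still following the protocol.

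The lost values would belong to subjects selected on adherence. For the MMRM endpoints (ppFEV1 and change in SwCl) the analysis would rest on missing at random, as SAP 8.3.1.3 states. For the two pooled SwCl response endpoints the GEE model would use the available data, and SAP 8.3.2.2 states no missing-data assumption for it. Endpoints through Week 52 would also lose follow-up, including the count of pulmonary exacerbations.

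**Working it through.** **1. Can 10.6 simply be read as stopping drug?** It may be meant that way, but no text says so. The genotype item in 9.9 sits in a list of reasons to stop drug and then adds removal from the study as a further step. SAP 8.2.1 tabulates discontinuation of treatment and of study separately. The two terms therefore name different actions, and a literal reading of 10.6 is open to a site.

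**2. The plan's own power.** Inputs (Protocol 12.1, SAP 6.2): 275 per arm, 10% drop-out, one-sided 0.025 for ppFEV1 and two-sided 0.05 for SwCl. Evaluable per arm: 275 × 0.9 = 247.5, taken as 247.
- ppFEV1 (SD 8, margin 3, true difference 0): SE = 8 × √(2/247) = 0.72; 3/0.72 = 4.17; noncentral t power 98.6%.
- SwCl (SD 14, difference 5): SE = 14 × √(2/247) = 1.26; 5/1.26 = 3.97; power 97.7%.

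Both agree with the stated figure of more than 95%. A further 2% loss per arm (242 evaluable) gives 98.4% and 97.5%; a further 5% (233) gives 98.1% and 97.0%. Power is not at issue.

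**3. What the exit visits recover.** Protocol 9.1.5 states: "Subjects who prematurely discontinue treatment will also be required to complete the Safety Follow-up Visit". Table 3-2 schedules in-clinic spirometry at both the Early Termination of Treatment (ETT) and Safety Follow-up visits, and SwCl at ETT only. SAP Appendix A assigns measurements by study day: Week 24 is (141, 211] for both measures; Week 16 is (85, 141] for spirometry and (71, 141] for SwCl.

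Let D be the study day of the last dose. Assume ETT on day D, Safety Follow-up on D + 28, and the Day 113 and Day 169 visits done only if they fall on or before D.
- ppFEV1: Week 24 is supplied if D + 28 ≥ 142, so D ≥ 114 (107 to 121 over the ±7-day window). Week 16 is supplied if D + 28 ≥ 86, so D ≥ 58 (51 to 65).
- SwCl: Week 24 is supplied if D ≥ 142, Week 16 if D ≥ 72.

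With D spread evenly over Days 1 to 168 (assumed):
- ppFEV1: both visits lost 57/168 = 33.9%; Week 24 only 56/168 = 33.3%; neither 55/168 = 32.7%. Mean share of the two-visit average lost: 0.339 + 0.333/2 = 0.506.
- SwCl: 71/168 = 42.3%, 70/168 = 41.7%, 27/168 = 16.1%. Mean share lost: 0.423 + 0.417/2 = 0.631.

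**4. Illustrative shift in the ppFEV1 difference.** Shift = (fraction of one arm removed) × (shortfall from the model's prediction) × (share lost). The documents supply neither of the first two. Assume 1% to 3% (275 × 0.01 = 2.75 to 275 × 0.03 = 8.25 subjects) and 5 points, in one arm only.
- With recovery: 0.01 × 5 × 0.506 = 0.025 to 0.03 × 5 × 0.506 = 0.076 points. The larger is 0.076/3 = 2.5% of the margin and 0.076/0.72 = 0.11 SE.
- Later removal, top of range: D from Day 29, share lost (29 + 56/2)/140 = 0.407, shift 0.061. D from Day 57, share lost (1 + 56/2)/112 = 0.259, shift 0.039.
- No recovery: 0.05 to 0.15 points (5% of the margin, 0.21 SE).
- Outer stress case, 5% removed and 12 points short: 0.05 × 12 = 0.6 without recovery (20% of the margin), or 0.6 × 0.506 = 0.30 with it.
- If both arms are affected equally, the shift is zero.

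**The case against.** The best defence is that this is loose wording in a protocol whose design is settled. Protocol 13.1.1.2 mentions leaving the study in a context of drug action, much as 10.6 does. Protocol 9.1.7 lists the ways participation ends and has no category for removal by the investigator for noncompliance. Section 9.9 is explicit and repeated elsewhere, and 10.6 asks the investigator only to consider the step, after education has failed. All of this stands and makes literal use of 10.6 less likely. It does not settle the matter, because no sentence makes 10.6 yield to 9.9. Nor do the triggers differ usefully: 10.6 concerns dosing and 9.9 concerns study procedures, but dosing is reasonably one of those procedures.

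Second, 10.6 is not limited to randomized subjects. Run-in ELX/TEZ/IVA is also study drug, and under 9.1.5.1 a Run-in subject who stops is not randomized and completes only the exit visits, as applicable. For that subject, leaving the study is essentially right. This stands, and the fix must separate the two periods.

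Third, SAP 8.3.1.4.1 and Appendix D plan a supplementary ppFEV1 analysis that sets every value after an intercurrent event to missing. That is a broader loss than 10.6 could cause, so it is informative. But it refits the same MMRM and does not test departures from missing at random.

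Fourth, the illustrative figures rest on assumptions that lean toward a larger effect. Noncompliance that persists despite education takes time to establish, so even timing from Day 1 overstates early loss. A one-arm effect is unlikely in a double-blind trial where all subjects take the same number of tablets. Both points stand.

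**Conclusion.** The conflict between 10.6 and the rest of the protocol is real for randomized subjects, and it touches data that the treatment-policy estimands would use. It is a minor internal inconsistency and a cheap improvement. Its size cannot be estimated from the documents. Under the 1% to 3%, 5-point scenarios with exit-visit recovery, the ppFEV1 shift stays below about 0.1 points. SwCl is somewhat less protected because it is not measured at Safety Follow-up.

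A reader might infer more, and the documents do not support it:
- That the non-inferiority result is biased or in doubt. The direction of any bias is unknown, the step is discretionary, and the margin lies about 4.2 SE from the planned difference of zero.
- That the trial is underpowered. Power stays well above the stated 95% under the added losses tried.
- That planned safety data are lost. The treatment-emergent period ends no later than 28 days after the last dose, so little or nothing is lost.
- That the protocol requires noncompliant subjects to be removed. It asks the investigator to consider it.

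**What to change.** In Protocol 10.6, replace the action on removing the subject from the study with: *discontinuing study drug treatment. Subjects who discontinue during the Treatment Period continue all scheduled visits per Sections 9.1.5.2 and 9.9 unless consent or assent is withdrawn; subjects who discontinue during the Run-in Period follow Section 9.1.5.1.*

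Whether and when to stop drug stays with the investigator, and the genotype rule in 9.9 is unchanged. The cost is this short wording change and a point in site training. The downside is that visits already in the schedule continue for a few noncompliant subjects. Some of them will still miss visits or withdraw consent, so not all of the loss is preventable.

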### **10.7 Blinding and Unblinding**

This is a double-blind study.

#### **10.7.1 Blinding**

All subjects (and their parents/caregivers/companions), site personnel (including the investigator, the site monitor, and the study team), and members of the Vertex study team will be blinded to the treatment codes.

Individuals who may be unblinded include only the following:

- Any site personnel for whom this information is important to ensure the safety of the subject in the event of a life-threatening medical emergency
- Any site personnel for whom this information is important to ensure the safety of the subject and her fetus in the event of a pregnancy
- Vertex Global Patient Safety (GPS) and Regulatory Affairs personnel to satisfy SAE processing and reporting regulations
- Vendor preparing the final (production) randomization list
- Vertex IWRS Manager
- Vertex Clinical Supply Chain

- DMC
- Vendor preparing the unblinded analysis of safety data for review by the DMC
- Analysts or vendor for modeling and simulations performing population PK modeling in preparation for regulatory submission(s)
- Bioanalytical contract research organization (CRO) analyzing PK samples and the Vertex Bioanalytical personnel who is not a member of the study team but reviews raw data from the Bioanalytical CRO. The Vertex Bioanalytical study team member will continue to be blinded.

#### Access to Spirometry and SwCl Results:

During the conduct of the study, the Vertex study team will not have access to the spirometry or SwCl results after the first dose of study drug on Day 1 of the Treatment Period, with the exception of spirometry related to adverse event reporting.

Shortly before any planned efficacy analysis is conducted, the spirometry and SwCl data will be reviewed for data cleaning purposes by a limited Vertex team that does not have access to the treatment codes.

Individual SwCl test results will not be disclosed to the study sites with the exception of the Screening Visit and Day -14 values. Subjects and their parents/caregivers/companions should not be informed of study-related spirometry results until Vertex has determined that the study has completed (i.e., clinical study report [CSR] finalization), regardless of whether the subject has prematurely discontinued treatment.

